## Background

Frailty is an age-related syndrome and describes the condition of older people's increased risk of adverse health outcomes, such as falls, institutionalization, hospitalization, disability and death. From The Irish Longitudinal study on Aging (TILDA) the prevalence of frailty in community dwelling adults aged 50 years and over in Ireland was 12.7% and the prevalence of pre-frailty was 31%. In people aged 65 year and over, the prevalence increased to 21.5% and 40% for pre-frailty.

In older people living with enduring or new onset mental health conditions, a recent systematic review suggested the prevalence of frailty in older people living with severe mental illness between 10.2 and 89.7% and was high in comparison to the general population (Pearson et al 2022). Individuals with a mental disorder had greater all-cause mortality hazards than the comparison group without mental disorders. The highest hazard ratio (3.65, 95% CI 2.40-5.54) was observed among individuals with bipolar disorder and frailty, relative to non-frail individuals without mental disorders.

Mental health is defined as a "state of well-being in which the individual realises his or her own abilities, can cope with the normal stresses of life, can work productively and fruitfully, and is able to make a contribution to his or her community" (WHO, 2001). Mental illness is described as the loss of mental health due to a mental disorder. The Mental Health Act 2001 defines mental illness as "a state of mind of a person which affects the person's thinking, perceiving, emotion or judgment and which seriously impairs the mental function of the person to the extent that he or she requires care or medical treatment in his or her own interest or in the interest of other persons" (Government of Ireland 2001, pg.10). The Older Adult mental health service cares for and provides treatment for new onset functional mental illness and dementia with complex behaviours for persons over the age of 65 years.

TILDA found frailty to have a bi directional relationship with mental health and older adults. People living with frailty are more likely to experience decline in mental health, lowering cognitive function and an increase in depressive symptoms. While people who live with enduring mental health may experience accelerated ageing and frailty due to mental distress and prolonged medication use or substance abuse.

There is a strong evidence base for reversal of frailty in the general population (Reference systematic reviews), interventions focus on exercise with or without protein based nutrition. However, there is very few studies that have translated this research to older peoples living with severe mental illness.

A recent RCT undertaken in Irish GP practices identified the acceptability and effectiveness of a low intensity intervention combining brief (<10 mins) advice on exercise and nutrition as with supporting information leaflets were acceptable to older people and helped to improve functional performance (Travers et al 2020). (Appendix 1 exercise and nutrition leaflets ).

In mental health consultations, advice on exercise and nutrition is often provided mental well-being benefits but it is not discussed in relation to building resilience and preventing frailty (Traver et al In press).

In this study we aim to test the acceptability and feasibility of replicating the above intervention for older patients attending MH consultations with the candidate ANP [AK].

### Aim

The aim of this study is to test the delivery of brief health promotion advice with supporting information leaflets as part of standard clinical consultation for older people attending a community mental health service.

Objectives: The main objectives are to;

- (a) to screen MH patients for frailty using validated tools the clinical frailty scale and SCAR-F
- (b) to test the feasibility of patient recruitment and data collection in the target population
- (c) determine the prevalence of frailty in older adults living with a mental health condition within an outpatient MH service
- (d) examine the acceptability of the brief health promotion advice and information leaflets as part of MH consultation
- (e) examine self-reported adherence to the exercise and nutrition advice at 1 and 3-month follow-up
- (f) Repeat frailty screening and overall physical and mental health at three month follow-up

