### Target Population

The target population is older adults attending mental health service aged 65 years and older. Age 65 years is the age for referral to the older adult mental health services. The Older adult mental health services provide care and treatment for people aged over 65's who develop new onset functional mental illness such as depression, severe anxiety or those with a diagnosis of dementia with behavioral and psychological problems requiring specialist intervention and care.

Patients with stable mental health conditions (during a recovery phase) will be identified from community mental health clinics and ANP community case load

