### Inclusion criteria

For the purpose of this study service users eligible for the study are:

- (a) Aged 65 years and older

- (b) Cognitive capacity to provide informed consent
- (c) Attending Older adult mental health services
- (d) MH team deem client stable and able to participate in intervention
- (e) Patient independently mobile and living in the community (may use a walk aid)(Clinical frailty Scale  $\leq 5$ )

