### Exclusion Criteria

For the purpose of this study

- (a) Service users with moderate advanced dementia will be excluded as the intervention is unsupervised.
- (b) Patients who cannot provide informed consent
- (c) Patients that cannot understand English or require a translator
- (d) Patients experience acute mental health crisis
- (e) Patients with significant restricted mobility, using Zimmer frame inside or outside their house (CFS $\geq 5$ )

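### Objective (c) promises the prevalence of frailty in an outpatient mental health service, but the plan can only give the proportion frail among 15-20 selected patients whose entry is itself limited by the Clinical Frailty Scale

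*Combined protocol and SAP*

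**What the plan says.** The Aim section lists six main objectives. Objective (c) is to "determine the prevalence of frailty in older adults living with a mental health condition within an outpatient MH service". Objective (a) is to screen patients with the CFS and SARC-F.

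The Target Population section describes a service for people aged 65 and over with new-onset functional illness, or "those with a diagnosis of dementia with behavioral and psychological problems requiring specialist intervention and care". It then narrows the source: "Patients with stable mental health conditions (during a recovery phase) will be identified from community mental health clinics" and from the nurse's own case load.

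The eligibility criteria narrow it further:

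- Inclusion (d): "MH team deem client stable and able to participate in intervention".
- Inclusion (e): "Patient independently mobile and living in the community (may use a walk aid)(Clinical frailty Scale" of 5 or below).
- Exclusion (a): "Service users with moderate advanced dementia will be excluded as the intervention is unsupervised".
- Exclusion (b): "Patients who cannot provide informed consent".
- Exclusion (c): "Patients that cannot understand English or require a translator".
- Exclusion (d): acute mental health crisis.
- Exclusion (e): significantly restricted mobility with use of a Zimmer frame, with CFS 5 or above in brackets.

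Under Obtaining Consent, the nurse and the team identify eligible patients. Under Data Collection, the questionnaire follows consent. The study log, described with the implementation outcomes, lists counts that begin with eligible patients invited. Sample size is 15-20, justified by feasibility. The Analysis section plans proportions and percentages and names no interval. The Outcomes section gives no CFS cut-off for frail.

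**The concern.** A prevalence needs a defined population and a count of cases within it. Objective (c) names people attending the service. The plan counts people who attend, are stable, can consent, walk independently, understand English, are approved by the team, and score low enough on the scale that is then used to measure frailty. Selecting on the measured quantity truncates its distribution, and recruiting more patients under the same criteria would not cure that.

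What is at stake is what the study may conclude. The Background cites a prevalence between 10.2% and 89.7% in older people with severe mental illness. A figure from this sample labelled as service prevalence could be set beside that range, although it describes a different population.

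**Working it through.** **1. Who can be counted.** Inclusion (e) requires CFS 5 or below, so scores 6-9 cannot enter the numerator or the denominator, however exclusion (e) is read. The Outcomes section says the CFS draws on comorbidity, function and cognition, so the exclusions for moderate or advanced dementia and for Zimmer-frame use also bear on the score. Stability, capacity, language and absence of crisis are not frailty limits and may remove frail and non-frail patients alike.

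**2. Can the loss be recovered?** Setting the sections side by side: eligible patients are identified first, data follow consent, and the log items start at eligible patients invited. Patients screened out on CFS appear nowhere, neither as scores nor as a count.

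**3. The CFS limit alone.** Assume that frail means CFS 5 or above (no cut-off is stated) and that CFS 5 is admitted. Let P be the true proportion frail and s the share of frail patients scoring exactly 5 (assumed). The enrolled proportion is P·s / (1 − P + P·s). The values of P are Background figures, used only as examples.

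| P | s = 0.25 | s = 0.50 | s = 0.75 |
|---|---|---|---|
| 10.2% | 2.8% | 5.4% | 7.9% |
| 21.5% | 6.4% | 12.0% | 17.0% |
| 89.7% | 68.5% | 81.3% | 86.7% |

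Every entry lies below P.

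**4. All criteria together.** Let f and g be the shares of frail and non-frail patients who stay eligible (both assumed), with enrolment random among the eligible. The enrolled proportion is p·f / (p·f + (1 − p)·g). With p = 21.5%, f = 0.75 and g = 0.50: 0.16125 / (0.16125 + 0.3925) = 29.1%. The full grid at p = 21.5%:

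| f | g = 1.00 | g = 0.75 | g = 0.50 |
|---|---|---|---|
| 0.75 | 17.0% | 21.5% | 29.1% |
| 0.50 | 12.0% | 15.4% | 21.5% |
| 0.25 | 6.4% | 8.4% | 12.0% |

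The figure is too low when f < g, right when f = g and too high when f > g. The documents fix neither f nor g.

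**5. Precision, a separate matter.** The 15-20 target has no precision calculation behind it to reproduce. Exact (Clopper-Pearson) 95% intervals at an observed 20% are 4.3-48.1% for 3/15 and 5.7-43.7% for 4/20, before any selection is considered.

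**The case against.** The best defence is objective (a). If patients are screened with the CFS and SARC-F, and if a CFS limit governs entry, somebody must be rated before enrolment, and nothing says those ratings are thrown away. That is fair as far as it goes. But no section says that all attenders are rated, that pre-entry ratings are kept, or that they form the denominator for (c). The plan as written does not deliver them.

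It can also be said that only moderate or advanced dementia is excluded, so milder dementia with capacity can remain, and that how far the mental health condition in (c) was meant to cover dementia is open. Both points stand. They narrow one strand of the selection and leave the CFS limit untouched.

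The retention shares are assumed and 21.5% is a general-population figure. The grid therefore shows only that the bias is undetermined. It does not estimate it.

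Finally, this is a feasibility study, and the Analysis section concedes a small sample. That remark is attached to the pre/post comparison and concerns size, not which population is counted.

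Three stronger readings are tempting, and the documents do not support them:

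- A reader might infer that the reported figure must be too low. Only the CFS limit taken alone has that direction.
- A reader might infer that the figure is 0% by construction. With frail taken as CFS 5 or above, that follows only if exclusion (e) is read as removing every patient at CFS 5 or above. It can equally be read as a mobility exclusion with the score as a gloss, and inclusion (e) admits CFS 5.
- A reader might infer that SARC-F escapes because no SARC-F limit applies at entry. Its components include assistance with walking, chair rise and stairs, on which the mobility criteria act, and it comes from the same enrolled patients.

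**Conclusion.** The point holds and should be fixed. Following the plan gives the proportion frail in a small sample truncated on the outcome, and that proportion cannot be reported as prevalence in the service. This rests on the wording of the objective, the eligibility criteria, the order of consent and data collection, and the listed log items. It needs no assumed cut-off. No net size or sign of bias can be given, and no item the plan lists would let a reader work it out. One of six objectives is affected. Feasibility, acceptability and adherence are not.

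**What to change.** Reword objective (c) to: *describe the CFS and SARC-F distribution among enrolled, stable, independently mobile patients*, and drop the claim to service prevalence. In the Analysis section, report the count at each CFS score, and SARC-F 4+ separately, each proportion with an exact 95% confidence interval. Counts by score let readers apply their own cut-off.

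This costs one sentence in the objectives and one in the analysis, with no new data, visits or consent. The study will then give no service prevalence figure, which the design cannot deliver anyway.

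If the sponsor wants that figure, the alternative is to record de-identified CFS scores for all attenders over a defined period, with a stated cut-off and denominator. That is a larger change. By n = 1.96²·p(1 − p)/d² with d = 0.10, a half-width of 10 percentage points needs 36 patients at p = 10.2% or 89.7%, 65 at 21.5% and 97 at 50%.

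Separately, inclusion (e) and exclusion (e) overlap at CFS 5 and must be reconciled. That is an edit to the eligibility criteria, additional to the two sentences above.

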### Target Population

The target population is older adults attending mental health service aged 65 years and older. Age 65 years is the age for referral to the older adult mental health services. The Older adult mental health services provide care and treatment for people aged over 65's who develop new onset functional mental illness such as depression, severe anxiety or those with a diagnosis of dementia with behavioral and psychological problems requiring specialist intervention and care.

Patients with stable mental health conditions (during a recovery phase) will be identified from community mental health clinics and ANP community case load

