### Intervention components

The intervention is delivered by the candidate ANP who is an experienced mental health nurse and is skilled in using motivational interviewing principles to support behaviour change. A normal part of the role is the provision of general health promotion advice for patients in clinics and their home. This aligns with the HSE policy on Making Every Contact Count (<https://www.hse.ie/eng/about/who/healthwellbeing/making-every-contact-count/>).

- Deliver brief Health Promotion advice on exercise and protein nutrition for muscle health to promote resilience and reduce risk of frailty
- Provide patients with information leaflets and clarify expectations for frequency of exercise (Appendix). The exercise and nutrition advise leaflets are used with permission of Travers et al 2022. Both leaflets were deigned based on extensive public patient involvement with older patients, physiotherapist and dietician. The exercises are low risk (use a chair for balance support, sit to stand exercises). Patients with impaired mobility, using Zimmer frame are excluded from study.
- One-month follow-up is undertaken via telephone (or face-to-face if visit scheduled as part of routine care). The one-month follow-up is to encourage adherence to

exercise and nutrition advice and examine adherence and feasibility of undertaking exercise and following diet advice.

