#### Data collection

The ANP completes the structured questionnaire with the patient in the MH clinic or patient home during routine clinical consultations. The one-month and three month follow-up via telephone or in the OPD clinic/persons' home as part of normal schedule of visits. No extra clinic or home visits are planned as part of the study.

The structured questionnaire used in this study has been developed by an expert group of geriatricians, and old age psychiatry and includes validated measures of frailty (see below)

This study tests the user acceptability of the intervention and the recruitment and data collection approach.

Ethical approval was obtained from Clinical Research Ethics Committee of the Cork Teaching Hospitals (CREC)

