#### Obtaining Consent

Participants provide written consent to the study. the ANP liaises with the Mental Health team to identify eligible patients and ensure the team are happy for the service user to be approached about the study.

Service Users receive an introduction letter and a copy of the patient information sheet informing them of the study and advising that they may be asked to participate in the study at their next outpatient appointment or home visit. The patient meets the data collector who explains the study, answer any questions and obtains written consent.

Participants are given the right to withdraw from participation should they wish to, as well as to opt out of answering questions. Participants have a right to withdraw without explanation. Patients provide permission to collect identifying information to allow follow-up. As soon as follow-up is complete, all identifying information is removed from the dataset so the data becomes de-identified and the participant is allocated a study ID.

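### No rule fixes which eligible patients are invited or in what order, and the log counts only those invited, so selective approach is possible and could not be detected

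*Combined protocol and SAP*

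**What the plan says.** Target Population defines the target as people aged 65 and over who attend the service, and says that those with stable conditions "will be identified from community mental health clinics and ANP community case load". Under Obtaining Consent, "the ANP liaises with the Mental Health team to identify eligible patients" and checks that the team is content for each person to be approached. An advance letter then tells service users that "they may be asked to participate in the study at their next outpatient appointment or home visit". One inclusion criterion is itself a team judgement: "MH team deem client stable and able to participate in intervention".

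Sample size gives a target of 15-20 patients, without a calculation. Study Design places recruitment in March to June 2023. The study log, described at the end of Outcomes under the implementation measures, counts eligible patients invited, refusals with reasons, consents, and completers at 1 and 3 months. It does not list patients who were eligible but not invited.

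Objective (b) in the Aim section is "to test the feasibility of patient recruitment and data collection in the target population"; objective (d) is acceptability.

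The ANP who helps to identify patients also has the later roles. "The intervention is delivered by the candidate ANP", and under Data collection "The ANP completes the structured questionnaire with the patient in the MH clinic or patient home during routine clinical consultations". Data management states that the data collector is unblinded.

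**The concern.** In most small pilots, loose recruitment wording is a side issue. Here recruitment is one of the things being tested, so the way invitees are chosen bears directly on a result. The plan names the sources of patients and the people who identify them, but it gives no consecutive, random or complete-invitation rule and no order of approach.

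Suppose the patients thought most likely to agree were approached first, and recruitment stopped at 20. Uptake would then describe those patients and not the population named in objective (b). Acceptability, retention and adherence could lean the same way, since they are measured only in those who enrol. A larger sample would not help, because this is bias and not imprecision. As the log starts at invitation, a reader of the final report could not tell whether 25 invitations came from 25 eligible patients or from 100.

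**Working it through.** The plan has no figure to reproduce: it gives no expected uptake, no eligible-pool size and no basis for the 15-20. The check is a reading of the text, followed by two illustrations. **Every rate and pool size below is an assumption**, except the upper recruitment target of 20.

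**Reading.** Target Population gives the source, and Obtaining Consent gives the people who identify patients and the team's agreement. The inclusion and exclusion criteria say who is eligible. The log records what happens after invitation. No section covers the step between being eligible and being invited.

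**Illustration 1: what the log can and cannot show.** Let 25 patients be invited and 20 consent. Let E be the number eligible, and let patients not invited consent at 40% if asked.

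- Uptake visible in the log = 20/25 = 80%, whatever E is.
- Uptake if all eligible patients had been invited = (20 + 0.40 × (E − 25)) / E.

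| Eligible (E) | Share invited | Calculation | Uptake across eligible | Log shows |
|---|---|---|---|---|
| 25 | 100% | 20/25 | 80% | 80% |
| 40 | 62.5% | (20 + 6)/40 | 65% | 80% |
| 60 | 42% | (20 + 14)/60 | 57% | 80% |
| 100 | 25% | (20 + 30)/100 | 50% | 80% |

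The gap runs from zero to 30 points, and the log looks the same throughout.

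**Illustration 2: partial and complete selection.** Let half of eligible patients be keen (80% consent, 90% of those enrolled find the advice acceptable) and half reluctant (30% and 60%). Let k be the keen share among those invited.

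- Uptake = 0.80k + 0.30(1 − k).
- Acceptability among enrolled = (0.80 × 0.90k + 0.30 × 0.60(1 − k)) / uptake.

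| k | Uptake | Acceptability among enrolled |
|---|---|---|
| 0.50 (no selection) | 0.40 + 0.15 = 55% | (0.36 + 0.09)/0.55 = 82% |
| 0.75 (partial) | 0.60 + 0.075 = 67.5% | (0.54 + 0.045)/0.675 = 87% |
| 1.00 (only keen invited) | 80% | 90% |

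If the keen share in the eligible pool is 30% or 70% instead of 50%, uptake without selection is 0.24 + 0.21 = 45% or 0.56 + 0.09 = 65%. Acceptability is (0.216 + 0.126)/0.45 = 76% or (0.504 + 0.054)/0.65 = 86%. Against complete selection (80% and 90%), the gap is 15 to 35 points for uptake and about 4 to 14 points for acceptability. Acceptability moves less because consent already filters out many reluctant patients, however they are invited.

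**Sampling error for scale.** The exact 95% interval is 52-96% for 12/15 and 56-94% for 16/20. These intervals do not include any selection bias.

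**The case against.** A reader might infer that the nurse hand-picks patients from their own case load, so that the results describe a hand-picked group. The documents do not support this, for four reasons.

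- The plan is silent on how invitees are chosen. It permits selection but does not state it.
- The ANP does not act alone. The team shares identification and must agree to each approach. This is a second filter and not a sampling rule, but it rules out a claim about one nurse's choice.
- The conditional phrase in the advance letter describes what patients are told. It suits a process in which the team may not agree or the patient may no longer be stable, and should not be read as a sampling rule.
- The last paragraph of Background names patients consulting the candidate ANP as the setting. Using that case load, and the prior relationship it brings, is therefore declared scope. The limits on stability, capacity and mobility are likewise stated eligibility.

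The size can also be challenged. The largest gaps need perfect recognition of keen patients or a pool much larger than the number invited. If nearly all eligible patients are invited, the bias is near zero. Analysis is descriptive, the plan sets no uptake or acceptability threshold that a shift could cross, and sampling error at 15-20 is already wide. The log does give uptake and refusal reasons among invitees.

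All of this stands, and it limits the claim to what may happen. It does not supply an invitation rule or make eligible patients who were not invited visible.

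**Conclusion.** The concern holds in a limited form. The plan has no rule for who is invited or in what order, and its log cannot show who was passed over. Uptake may therefore look better than in the target population, and acceptability, retention and adherence may do so to a lesser extent. The size cannot be known from the documents. The assumed scenarios give 0 to 35 points for uptake and 0 to 14 for acceptability; retention and adherence were not quantified. The lower end applies when invitation is close to complete.

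Two stronger conclusions do not follow: that selective approach will occur, and that the nurse's several roles show that it did. Those roles are a reason to want a transparent invitation step and are not evidence of bias. The change is worth making because recruitment is itself an objective and the remedy is cheap.

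**What to change.** In Target Population, add wording such as:

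> From the first recruitment day, all patients on the clinic lists and the ANP case load who meet the criteria, and whom the team agrees may be approached, are invited consecutively in order of next scheduled appointment or visit, until 20 have consented or the March-June 2023 window closes.

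In the study-log paragraph, extend the log to eligible patients not invited, with the reason (including that the team did not agree) and the source (clinic or ANP case load). Report uptake against all eligible patients reached in that sequence as well as against those invited. In the first illustration, with 40 eligible patients reached, this would show 20/40 = 50% beside 20/25 = 80%, with reasons for the other 15.

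Leave the conditional wording of the advance letter as it is. A promise that every recipient will be asked would conflict with the team-agreement step. Report source as descriptive counts only and do not compare sources: with about 10 patients in each, 8/10 has an exact 95% interval of roughly 44-97%.

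The cost is protocol wording and a few log columns, with no extra visits. The ANP gives up some discretion, recruitment may be slightly slower, and reported uptake may be lower. The team's judgement on whom to approach is kept.
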